	
Eligible subjects will undergo a two-week Medical Documentation Screening period to confirm resistant hypertension (SBP <math>\geq</math> 155mmHg) while on maximum tolerable doses of <math>\geq</math> three anti-hypertensive medications from at least three classes of drugs, one of which must be a diuretic.
 
There must be documented clinical evidence to support likelihood of angiographic findings <math>> 80\%</math> whether it is Duplex Ultrasound (DUS), Computed Tomography angiogram (CTa), Magnetic Resonance angiogram (MRa) or other medical evidence. After meeting screening and clinical eligibility criteria, subjects will undergo a baseline assessment for angiographic eligibility. After angiographic documentation of a <math>\geq 80\%</math> diameter renal artery stenosis or Fraction Flow Reserve (FFR) <math>< 0.8</math> is confirmed, the subject may be enrolled in the trial by placement of the investigational device.
 
The 9-month visit will include a follow-up DUS of the target renal artery. If the DUS is non-diagnostic due to an imaging quality problem, such as overlying bowel gas or body habitus, a second DUS may be attempted. If the DUS is indicative of <math>\geq 60\%</math> stenosis as determined by the core laboratory, or the second DUS remains non-diagnostic, a contrast angiogram will be used to assess the degree of restenosis of the covered stent(s).
 
Clinical follow-up visits will be required for all enrolled subjects at 30-days, 9-months, 12-months, 24-months, and 36-months. A 6-month and 18-month visit will occur via telephone to collect medication usage and Adverse Events (AEs) only. The 36-month clinic office visit will be required as the final safety visit.

SUBJECT POPULATION	Subjects who are candidates for a renal artery revascularization with $\geq 80\%$ visual stenosis and have resistant hypertension with $\geq 155\text{mmHg}$ while on $\geq 3$ anti-hypertensive medications from at least 3 classes of drugs, one of which must be a diuretic.
NUMBER OF SUBJECTS	Up to 138 subjects will be enrolled in this trial.
ESTIMATED TRIAL DURATION	The trial duration is projected for 60 months.

ESTIMATED SUBJECT DURATION	Each subject is expected to be enrolled and followed for a total of 36 months.

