## APPENDIX 4: SCHEDULE OF EVENTS

	(-14)-Days (Medical Documentation Screening period)  Prior to Procedure	(-7)-Days   Prior to Procedure	Day 0  Procedure	30-Days (+14/-7 Days)  Office Visit	6-Months (+/-30 Days)  Phone Call	9-Months (+/-30 Days)  Office Visit	12-Months (+/- 30 Days)  Office Visit	18-Months (+/-30 Days)  Phone Call	24-Months (+/- 60 Days)  Office Visit	36-Months (+/- 60 Days)  Office Visit
Informed Consent	X									
General Entry Criteria	X									
Angiographic Entry Criteria			X							
Demographics and Medical History	X									
Weight (Kg)/ Height (cm)	X									
Vital Signs	X		X	X		X	X		X	X
BP Assessment	X 	X 	X	X		X	X		X	X
Laboratory Assessments	X 		X 	X 		X 				
Test for Proteinuria	X 									
Physical Exam	X		X	X		X	X		X	X
Pregnancy Test	X 		X 							
iCAST™ RX Stent System Placement			X							
Duplex Ultrasound				X		X				
Angiography			X 			X 				
Concomitant Medications	X	X	X	X	X	X	X	X	X	X
Adverse Events	X	X	X	X	X	X	X	X	X	X

A minimum of two office visits are required within the 14-day Medical Documentation Screening period. If the procedure is scheduled > 14 days from the first office visit, subjects should return every two weeks (+/- 3 days) for BP assessments and monitoring.

Chem12 panel which includes: Glucose, Calcium, Albumin, Total protein, Sodium, Potassium, CO2, Chloride, BUN, creatinine, ALP, ALT, AST, and bilirubin.

Test for proteinuria should be completed for subjects during Step 2 of the Medical Documentation Screening Period.

Pregnancy test required at screening and on the day of procedure for females of childbearing potential only.

All subjects must have angiography to determine percent diameter stenosis prior to treatment and at 9-months (if DUS indicates ≥ 60% stenosis).

AE collection (serious and non-serious) will begin upon completion of the ICF process through the 9-month follow-up visit, thereafter only SAEs and UADEs will be recorded.

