6.2 Changes from the Analyses Planned in the Protocol/CIP

Due to the early termination of enrollment for Protocol/CIP No. iCAST™ RX-ARAS-001, all inferential analysis should be interpreted as descriptive and will be carried out in an exploratory manner.

The following changes were applied:

1. Missing data will not be imputed.
2. Sensitivity analysis will be limited to evaluating the primary analysis results using the per protocol population.
3. Supportive analysis of the revascularization information using a time to event approach will be performed.

Confidential

7. BASELINE, EFFICACY and SAFETY EVALUATIONS

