9.9.1. Primary Patency Analysis

The primary endpoint will be the cumulative incidence of primary patency at 9-months of study computed as the number of subjects with primary patency at 9-months divided by the number of subjects in the ITT population. An exact binomial one-sided 95% confidence interval will be constructed and the upper limit compared to the Performance Goal equal to 70%. A p-value for the one-sided exact test of the difference between the observed rate and the Performance Goal will be presented. The primary analysis will be analyzed with observed data only.

A planned subgroup analysis of the primary functional endpoint will be performed (details are provided in section 9.9.4

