9.11.11. Revascularization

The total number of subjects with additional treatments to the target vessel will be summarized by counts and percents. In addition, the cumulative probability of target vessel revascularization by 9-months will be computed using the life-table method.

The following SAS code will be used:

Amendment #1: 15Jul13

```
PROC LIFETEST DATA = ADTT;  
  TIME DURATION * CENSOR (0);  
  STRATA TREAT;  
  RUN;
```

Time to revascularization is defined as the time from date of procedure until date of revascularization. For each lesion that has not undergone revascularization, it will be censored at the time of last contact date known to be alive (contacts considered in the determination of last contact date include adverse event date, vital signs, and last known alive date from Study Exit page of eCRF).

Where:

Time to Revascularization = (Date of Revascularization – Date of Procedure +1)

In order to provide visualization of the estimated probability of an event, a cumulative incidence plot of the target vessel revascularization will be presented.

A subject listing with the revascularization information will be also presented and include:

- Subject ID/Lesion
- Date of procedure
- Number of target/non-target lesions treated
- Indication for revascularization
- Lesion Location
- Lesion Type
- Pre-procedure % diameter stenosis
- % stenosis

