9.11.13. Mortality

The number and percent of all cause deaths will be reported throughout the study or at the cutoff date for DSMB. The Kaplan-Meier estimate of the death free-survival curve by 9-months of study follow-up will be presented. Death-free survival is defined as the time (months) from the date of the procedure (stent placement) to the date of death of any cause. For each patient that has not known to have died, these will be censored at the time of last contact date known to be alive (contacts considered in the determination of last contact date include adverse event date, vital signs, and last known alive date from Study Exit page of eCRF).

A detailed listing of deaths will be provided and include: subject ID, date of procedure, date of death, relatedness to the study device, primary cause of death, investigator's comments.

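### The 9-month revascularization estimate censors lesions at the date the subject was last known alive, so a Study Exit alive date can add event-free time with no information on re-intervention

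*SAP*

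**What the plan says.** SAP 9.11.11 plans a 9-month estimate: "the cumulative probability of target vessel revascularization by 9-months will be computed using the life-table method". For lesions without an event the rule is "For each lesion that has not undergone revascularization, it will be censored at the time of last contact date known to be alive". A parenthesis defines the date: "contacts considered in the determination of last contact date include adverse event date, vital signs, and last known alive date from Study Exit page".

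SAP 9.11.13 applies the same rule to all-cause death. Subjects not known to have died are handled in these words: "these will be censored at the time of last contact date known to be alive". The list of contacts is identical.

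SAP 6.2 describes the role of the analysis: "Supportive analysis of the revascularization information using a time to event approach will be performed". For the primary patency proportion, SAP 9.9.1 says "The primary analysis will be analyzed with observed data only".

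The schedule of events places vital signs at day 0, day 30 and 9 months within the period that matters here. The only scheduled contact between day 30 and 9 months is a phone call. The Protocol Summary says of the calls: "A 6-month and 18-month visit will occur via telephone to collect medication usage and Adverse Events (AEs) only". On adverse events, Protocol Appendix 4 says "AE collection (serious and non-serious) will begin upon completion of the ICF process through the 9-month follow-up visit".

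**The concern.** A date on which a subject is known to be alive is the right censoring date for death, because it settles whether the event has happened. It does not settle whether a stent has been re-treated. SAP 9.11.11 does not require re-intervention status to be known on the censoring date.

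The three listed contacts differ in this respect. A visit with vital signs also collects adverse events, so a re-intervention would normally come to light there, and an adverse event date comes from the same kind of review. The Study Exit alive date may rest on nothing more than knowledge that the subject is living. If it falls after the last real check, the interval between them enters the risk set as event-free time in which no event could have been recorded. The error has one direction: the estimated probability is too low.

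There is a smaller gap on the other side. The 6-month call asks about adverse events but is not on the list. A subject reached then with nothing to report, and with no later listed contact, would on a literal reading be censored back at the day-30 visit although event-free status was established to about day 182.

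What is at stake is the accuracy of a supportive, descriptive estimate. It has some weight because SAP 6.2 drops imputation and limits sensitivity analysis to the per-protocol population, which leaves this as the remaining analysis that can use incomplete follow-up.

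**Working it through.** The documents give no figure for the effect of the censoring rule, so there is none to reproduce. The calculation below sizes it under stated assumptions.

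**Inputs**
- True 9-month rate p = 8.5%. This is the TLR performance goal in SAP 9.10.1, borrowed as an assumed rate for revascularization; range 5% to 15%.
- Share of lesions affected q = 10%, the planned attrition in SAP 5.5; range 5% to 20%.
- Day of last real check on re-intervention L: day 30 (the visit) or day 182 (target day of the 6-month call, SAP 7.4).
- 9 months = day 273 (SAP 7.4).
- Number of lesions, for scale only: 68 subjects (SAP 6.1) × 1.2 lesions per subject (SAP 5.2) = 81.6, about 82. The 1.2 comes from another trial.
- Constant hazard, loss unrelated to outcome, and every affected subject having an exit alive date at or after day 273. The last of these is a worst case.

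**Formulas**
- Hazard: λ = −ln(1 − p)/273 = 0.08883/273 = 0.0003254 per day.
- Probability that an event has occurred, and so is seen, by day L: g(L) = 1 − exp(−λL).
- Expected estimate under the SAP rule: (1 − q)p + q·g(L).
- Expected estimate when censoring at the last real check: p.

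**Base case, p = 8.5%, q = 10%**
- L = 30: g = 0.00971. Estimate = 0.9 × 0.085 + 0.1 × 0.00971 = 0.0775, which is 0.75 points low.
- L = 182: g = 0.0575. Estimate = 0.0765 + 0.1 × 0.0575 = 0.0823, which is 0.27 points low.

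**Underestimate over the range (percentage points)**

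| True rate | q | L = day 182 | L = day 30 |
|---|---|---|---|
| 5% | 5% | 0.08 | 0.22 |
| 5% | 10% | 0.16 | 0.44 |
| 5% | 20% | 0.33 | 0.89 |
| 8.5% | 5% | 0.14 | 0.38 |
| 8.5% | 10% | 0.27 | 0.75 |
| 8.5% | 20% | 0.55 | 1.51 |
| 15% | 5% | 0.24 | 0.66 |
| 15% | 10% | 0.47 | 1.32 |
| 15% | 20% | 0.95 | 2.65 |

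Over the whole table this is about 0.1 to 2.2 lesions out of 82.

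**Loss spread over time.** If L is uniform between days 30 and 180, the average of g is 1 − [exp(−30λ) − exp(−180λ)]/(150λ) = 0.0335 at p = 8.5%. The estimate is then 0.0765 + 0.1 × 0.0335 = 7.98% for q = 10%, and 0.068 + 0.2 × 0.0335 = 7.47% for q = 20%. A Kaplan-Meier simulation with 68 units gave 8.0% and 7.5%. Censoring at the date of loss in the same simulation gave 8.6% and 8.5%, which recovers the true rate within simulation error.

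**Scale.** The binomial standard error at 8.5% with 68 units is √(0.085 × 0.915/68) = 3.4 points.

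**Death treated as censoring.** Protocol Table 6 lists death at under 6% without a time frame. Taking 6% by 9 months as an assumption, a = −ln(0.915) = 0.0888 and b = −ln(0.94) = 0.0619. The cumulative incidence with death as a competing event is a/(a + b) × (1 − 0.915 × 0.94) = 0.589 × 0.140 = 8.25%, against 8.50% when deaths are censored.

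**The case against.** The strongest reply is that the rule is mostly sound in practice. Two of the three listed contacts do inform on re-intervention, so only the exit-page date can add uninformed time. The documents do not describe a search for vital status after loss of contact, nor how the exit date is obtained. If it is always recorded at an adverse event review, there is no such bias. This stands, and it is why the figures above are conditional on an assumed worst case.

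The list is introduced as what the contacts include, so it may not be exhaustive, and the phone call may be meant to count. That is possible, but then the date is undefined and still needs wording. The other omissions matter little. Scheduled duplex ultrasound falls at visits that record vital signs, and the 18-month call cannot affect a 9-month estimate.

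The two faults pull in opposite directions. Censoring at day 30 a subject who was event-free at the 6-month call discards good event-free time and pushes the estimate up. It affects only subjects lost between that call and the 9-month visit with no later listed contact. This part is not quantified, so the net direction across both faults is not established. What is established is the direction of the exit-date part.

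A reader might infer that the primary result is biased, because SAP 7.4 speaks of a supportive time-to-event analysis of the primary efficacy endpoint. The documents do not support that. Section 9.11.11 estimates target vessel revascularization, whereas patency also fails on total occlusion. The patency proportion uses observed data, and the TLR comparison in 9.10.1 uses an exact binomial interval. Neither calls on this censoring date. A reader might also infer that all time after loss counts as success. It does not: the lesion leaves the risk set at the alive date. That the sentence was carried over from the mortality section is plausible from the matching words but not shown.

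**Conclusion.** The point holds in a limited form. The SAP states a censoring date that fits death and does not fit a non-fatal event. Through the Study Exit date, it can bias the supportive 9-month revascularization probability downward. At a true 8.5%, with 10% of lesions affected and all of those subjects later known alive at 9 months, the underestimate is about 0.3 to 0.75 points. Over true rates of 5% to 15% and 5% to 20% of lesions affected, it runs from 0.08 to 2.65 points. These figures assume constant hazard and loss unrelated to outcome. They shrink if fewer lost subjects have a later alive date, and reach zero if that date is also a date of ascertainment.

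Against a standard error of about 3.4 points the base-case effect is small, and SAP sections 2 and 6.2 make all inference descriptive after enrollment stopped at 68. It is still worth correcting, because the exit-date error always favours the device and the plan can remove it by wording.

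**What to change.** In SAP 9.11.11, censor a lesion without revascularization at the last contact at which its re-intervention status was ascertained: clinic visit, phone call, adverse event review, duplex ultrasound or angiogram. Use the last-known-alive date for the mortality analysis in 9.11.13 only.

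Optionally, treat death as a competing event in the plot labelled cumulative incidence. The effect is small (0.25 points under the assumed 6%), and the documents give no 9-month death rate.

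The cost is a reworded sentence in the SAP and a revised censoring variable, built from follow-up contacts that the trial already makes. Whether every such date is held in the database cannot be confirmed from the documents. The estimate may be slightly less favourable and its interval slightly wider.

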9.11.12. Extent of Device Exposure**9.11.12.1. Extent of Exposure**

The total number of study days (device exposure – measured as total days on study after procedure) will be summarized using descriptive statistics (n, mean, standard deviation, median, min and max) using the ITT analysis population.

9.11.13. Mortality

The number and percent of all cause deaths will be reported throughout the study or at the cutoff date for DSMB. The Kaplan-Meier estimate of the death free-survival curve by 9-months of study follow-up will be presented. Death-free survival is defined as the time (months) from the date of the procedure (stent placement) to the date of death of any cause. For each patient that has not known to have died, these will be censored at the time of last contact date known to be alive (contacts considered in the determination of last contact date include adverse event date, vital signs, and last known alive date from Study Exit page of eCRF).

A detailed listing of deaths will be provided and include: subject ID, date of procedure, date of death, relatedness to the study device, primary cause of death, investigator's comments.

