### **3.0 TRIAL DESIGN AND POPULATION**

This is a prospective, single-arm, multicenter clinical trial that will take place at up to 25 US/OUS sites. Primary endpoints have been determined to show the safety, effectiveness, and clinical outcomes of the iCAST™ RX Stent System. Safety and effectiveness will be evaluated based on the primary patency rate at 9-months on a per lesion basis evaluated against a performance goal of published studies with bare-metal stents. The primary clinical endpoint will assess the improvement in systolic blood pressure at 9-months as compared to baseline systolic blood pressure.

Eligible subjects will undergo a two-week Medical Documentation Screening period to confirm resistant hypertension (SBP  $\geq$  155mmHg) while on maximum tolerable dose of  $\geq$  three anti-hypertensive medications from at least three classes of drugs, one of which must be a diuretic.

There must be documented clinical evidence to support likelihood of angiographic findings  $>$  80% whether it is DUS, CTa, MRa or other medical evidence. After meeting screening and clinical eligibility criteria, subjects will undergo a baseline assessment for angiographic eligibility. After angiographic documentation of a  $\geq$  80% diameter renal artery stenosis or FFR  $<$  0.8 is confirmed the subject may be enrolled in the trial by placement of the investigational device.

The 9-month visit will include a follow-up DUS of the target renal artery. If the DUS is non-diagnostic due to an imaging problem, such as overlying bowel gas or body habitus, a second DUS may be attempted. If the DUS is indicative of  $\geq$  60% stenosis as determined by the core laboratory, or the second DUS remains non-diagnostic, a contrast angiogram will be used to assess the degree of restenosis of the covered stent(s).

Clinical follow-up visits will be required for all enrolled subjects at 30-days, 9-months, 12-months, 24-months and 36-months. A 6-month and 18-month visit will occur via telephone to

collect medication usage and AEs only. The 36-month clinic office visit will be required as the final safety visit.

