6. CHANGES IN THE CONDUCT OF THE STUDY OR PLANNED ANALYSES

6.1 Changes in the Conduct of the Study

The enrollment for Protocol/CIP No. iCAST™ RX-ARAS-001 has been terminated after 68 subjects were screened and enrolled in the study as of November 2017. Enrolled subjects will be followed up to study completion.

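### After month 9 the SAP names no numerical, censoring-adjusted estimate of death or target-vessel revascularization, although follow-up runs to month 36

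*SAP*

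**What the plan says.** **Death (SAP 9.11.13).** Two outputs are named. One is crude: "The number and percent of all cause deaths will be reported throughout the study or at the cutoff date for DSMB". The other is adjusted for censoring but stops early: "The Kaplan-Meier estimate of the death free-survival curve by 9-months of study follow-up will be presented". The section defines time to death and censors survivors at last contact, so the machinery for a longer estimate is already there.

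**Target-vessel revascularization (SAP 9.11.11).** Three outputs are named:
- a crude one: "The total number of subjects with additional treatments to the target vessel will be summarized by counts and percents";
- a probability at one time: "the cumulative probability of target vessel revascularization by 9-months will be computed using the life-table method";
- a figure without a stated horizon: "a cumulative incidence plot of the target vessel revascularization will be presented".

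The censoring rule has no cut at month 9: "For each lesion that has not undergone revascularization, it will be censored at the time of last contact date known to be alive". Neither has the PROC LIFETEST code shown there.

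**MAE.** SAP section 4 asks for MAE, which include procedure- or device-related death and clinically driven target lesion revascularization, at 30 days and 9, 12, 24 and 36 months. SAP 7.6.2 computes it as subjects with an MAE divided by the ITT count.

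**Follow-up.** Protocol 3.0 states: "The 36-month clinic office visit will be required as the final safety visit". SAP 6.1 keeps this after enrolment stopped at 68 subjects: "Enrolled subjects will be followed up to study completion". SAP 8.5 has the Clinical Events Committee rule on every death in the trial. SAP 7.2 distinguishes a 9-month analysis from a final one.

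**The concern.** The death analysis that allows for incomplete follow-up covers the first 9 of 36 months. For the other 27 months the plan gives a percentage of the ITT population, in which a subject who withdraws at month 10 counts the same as one seen alive at month 36. For revascularization the only named probability also sits at month 9, and the late MAE report uses the same crude fraction.

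The late period matters to this device. Protocol 1.0 names restenosis as the main concern after stenting and says it may progress to occlusion and kidney loss. The trial now supports description only, so the description of late safety should not be biased in a known direction when the data to avoid this are already collected.

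**Working it through.** **Is a later estimate named anywhere else?**
- SAP 8.1 promises Kaplan-Meier estimates at whichever time points are indicated, plus a curve over time. For death and revascularization the only time point indicated is month 9, and SAP 9.11.13 ties the death curve itself to 9 months.
- SAP 9.10.3 allows a time-to-event summary of other secondary endpoints where suitable, but assigns it to no endpoint or time.
- Protocol 5.3.1 asks for survival curves with confidence intervals for time-to-event secondary endpoints, but does not name all-cause death or a 36-month horizon.

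So no section names a censoring-adjusted number for either event at 12, 24 or 36 months.

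**Size.** The plan states no figure for death or revascularization after month 9, so there is none to reproduce. Inputs:
- *N* = 68 (SAP 6.1).
- *M*, the true 36-month risk: assumed 6%, 10% or 15%. Protocol Table 6 lists death at below 6%, without a time frame.
- *L*, the loss by month 36: not given, so assumed 0% to 40%. The 10% attrition in Protocol 5.2 is for the 9-month endpoint. Carried forward unchanged, it would give 1 − 0.9⁴ = 34.4%.
- Constant event and loss hazards, with loss unrelated to risk.

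The Kaplan-Meier target is *M*. The expected crude fraction is

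crude = ln(1−*M*) / [ln(1−*M*) + ln(1−*L*)] × [1 − (1−*M*)(1−*L*)]

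For *M* = 10%, *L* = 10%: 0.5 × (1 − 0.81) = 9.5%. For *M* = 10%, *L* = 34.39%: 0.2 × (1 − 0.9⁵) = 0.2 × 0.4095 = 8.2%.

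| Loss by month 36 | Crude if true 6% | Crude if true 10% | Crude if true 15% | Crude / true | Shortfall at true 10%, N = 68 |
|---|---|---|---|---|---|
| 0% | 6.0% | 10.0% | 15.0% | 1.00 | 0 |
| 10% | 5.7% | 9.5% | 14.3% | 0.95 | 0.3 subjects |
| 20% | 5.4% | 9.0% | 13.5% | 0.90 | 0.7 |
| 34.4% | 4.9% | 8.2% | 12.3% | 0.82 | 1.2 |
| 40% | 4.7% | 7.9% | 11.8% | 0.79 | 1.5 |

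**What the 9-month estimate leaves out.** With *M* = 10% and a constant hazard, the 9-month estimate is 1 − 0.9^(9/36) = 2.6%, so 1 − 2.6/10 = 74% of the 36-month events fall later.

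**Why revascularization needs a different estimator.** SAP 9.11.11 treats death as ordinary censoring. Suppose 36-month mortality is 10%, the revascularization risk without death is 10%, and nobody is lost. The share actually revascularized is 0.5 × (1 − 0.81) = 9.5%, while one minus Kaplan-Meier gives 10%. Extending the present method unchanged would therefore err upward.

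**The case against.** A reader might infer that Kaplan-Meier estimates of both events stop at month 9 and that late stent failure gets only crude percentages. The documents do not support this for revascularization. SAP 9.11.11 speaks of a life-table method, its plot has no stated horizon, and its censoring rule and code would let the curve run to the end of follow-up. What is missing is a named number, interval and number at risk after month 9, and a stated plot horizon.

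A reader might also infer that revascularization is captured equally well to month 36. The schedules (Protocol Appendix 4, SAP 7.1) show no ultrasound or angiography after month 9 and record only serious adverse events and unanticipated adverse device effects from then on. A better estimator does not repair thinner capture.

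The strongest case for leaving the plan alone is that little depends on it. SAP sections 2 and 6.2 declare all inference descriptive, and no performance goal attaches to a late death or revascularization figure. The gap is about one subject, while the standard error of a 10% proportion at N = 68 is √(0.1 × 0.9 / 68) = 3.6 percentage points. SAP 9.1 shows observed and expected visits, SAP 9.11.13 lists deaths with dates, and display details are left to table mock-ups that are not in the documents.

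Most of that stands and sets the weight of the point. It does not remove the gap: the error runs one way, listings leave the calculation to the reader, and the SAP should itself name its main late-safety summaries.

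**Conclusion.** The point holds in limited form. For death, the plan as written gives only a crude percentage after month 9. For revascularization, it names no numerical estimate after month 9 and leaves the plot horizon open. The late MAE report is crude.

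Under assumed losses of 10% to 40% by month 36, crude figures would be about 0.95 to 0.79 of the true risk. With no loss there is no difference. The range rests on constant hazards, loss unrelated to risk, and loss rates the documents do not give. At 68 subjects the effect is small next to sampling error. The primary endpoints and performance goals do not depend on it.

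**What to change.** In SAP 9.11.13, extend the Kaplan-Meier estimate of death to 36 months at the final analysis, with 95% confidence intervals and numbers at risk at 30 days and 9, 12, 24 and 36 months.

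In SAP 9.11.11:
- report cumulative incidence of target-vessel revascularization at the same times, with death as a competing event;
- state the plot horizon;
- reconcile the life-table wording with the PROC LIFETEST code, which sets no method option;
- note that after month 9 there is no scheduled imaging and only serious adverse events and unanticipated adverse device effects are recorded, so late revascularization may be under-captured.

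Keep the 9-month figures as the first report. The cost is SAP wording and a little programming, with no new data. Intervals at late time points will be wide.
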